session × 3 treatment sessions [Days 1, 22, and 43] for a maximum total dose of 5.04 mg). Participants in Cohort 6 will receive a maximum dose of up to 0.42 mg of QWO (CCH-aaes) on the control side and a maximum dose of up to 0.21 mg of QWO (CCH-aaes) on the investigational side per treatment session for 2 treatment sessions (Days 1 and 43) for a maximum total dose of 1.26 mg. All participants in Cohort 7 will receive a maximum dose of up to 0.84 mg of OWO (CCH-aaes) on the control side and a maximum dose of up to 0.84 mg of QWO (CCH-aaes) to the investigational side per treatment session × 3 treatment sessions for a maximum total dose of 5.04 mg. Participants in Cohort 7a will have the investigational side treated with QWO (CCH-aaes) on Days 1, 22, and 43 with the control side treated with QWO (CCH-aaes) on Days 22, 43 and 64. Treatment will be staggered for participants in Cohort 7b vs Cohort 7a. Participants in Cohort 7b will have the investigational side treated on Days 22, 43, and 64 and the control side treated on Days 1, 22, and 43. Tranexamic acid will be provided by the sponsor and self-administered by all participants enrolled in Cohort 7. Participants in Cohort 7a will take tranexamic acid 1300 mg orally TID for 5 days (prior to the day of the first injection of QWO (CCH-aaes) of the investigational buttock (Day -1), the day of the first injection (Day 1). and for the 3 days following the first injection (Days 2 to 4). Participants in Cohort 7b will take tranexamic acid orally TID for 5 days (prior to the day of the second injection on Day 21, the day of the second injection (Day 22) and for the 3 days following the second injection (Day 23 to Day 25).

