Support for the use of more dilute concentrations of QWO (CCH-aaes) is derived from Studies EN3835-209 and EN3835-224 (see Section 3.3.3). Support for half-dose and quarter-dose of QWO (CCH-aaes) is derived from Study AUX-CC-831 (see Section 3.3.5). Study AUX-CC-831 tested QWO (CCH-aaes) at 0.06 mg, 0.48 mg, and 0.84 mg. The study demonstrated improvement in a variety of parameters with the 0.06 mg dose, and investigators determined that approximately 45% of participants had improvement in their cellulite, although it was not statistically significant. The 0.48 mg dose was associated with statistically significant improvements. Therefore, in this study, Cohort 6 will evaluate a QWO (CCH-aaes) dose between the lowest and the middle dose given in Study AUX-CC-831, to determine whether there will be a decrease in bruising while experiencing an improvement in cellulite.

Administering QWO (CCH-aaes) using a shallower depth of injection (¼ inch) rather than the labeled depth (½ inch) injection is supported by the results of a study conducted by Whipple et al (2021). Using ultrasound, the investigators identified the depth of the fibrous septa causing cellulite and delineated their anatomical orientation. The average skin thickness in 92 buttock dimples was 0.28 cm and the depth of superficial fascia was 0.84 cm. A depth of a ¼-inch

(0.64-cm) injection would place the tip of the needle within the superficial subcutaneous tissue. The majority of fascial bands originate from the superficial fascia and therefore using a shallower depth of injection could facilitate the lysis of the causative bands while potentially avoiding more expanded vasculature when using a deeper injection. This approach is further supported by the method used in a subcision technique for cellulite, which uses a depth of 0.06 cm to 0.10 cm (Green and Cohen, 2015).

In Study EN3835-224, a more dilute concentration of QWO (CCH-aaes) was used to treat cellulite. In this study's 2-aliquot cohort, a concentration of QWO (CCH-aaes) 0.05 mg/mL, combined with injecting QWO (CCH-aaes) at ¼-inch and ½-inch depths, was demonstrated to be safe and well-tolerated with a low incidence of discoloration. In this study (APHRODITE-1), Cohorts 2 (~5-fold dilution) and 4 (~2.5-fold dilution) will evaluate using lower concentrations of QWO (CCH-aaes). Cohort 3 will evaluate using a shallower depth of injection. Taken together, this study will attempt to isolate the impact of each of these variables on bruising.

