	• Cohorts 7a and 7b: The proportion of participants within each cohort (ie, 7a and 7b) whose left buttock (investigational side) demonstrates at least 1-level lower score versus the right buttock (control side), on the IABSS, by corresponding treatment visit by buttock (first dose of QWO [CCH-aaes] on the investigational buttock with tranexamic acid vs the first dose of QWO [CCH-aaes] without tranexamic acid on the control side; second dose of QWO [CCH-aaes] on the investigational buttock vs second dose of QWO [CCH-aaes] on the control side; third dose of QWO [CCH-aaes] on the investigational side vs third dose of QWO [CCH-aaes] on the control side); and at each follow up visit thereafter.
To assess the level of aesthetic improvement of cellulite after treatment with QWO (CCH-aaes).	• The proportion of participants with an improved (+1 or better) score on the Investigator-Global Aesthetic Improvement Scale (I-GAIS) by treatment area at Days 22, 43, 64, 90, 135 and 180 Visits. The I-GAIS is a 7-point scale ranging from +3 (very much improved) to -3 (very much worse).
To assess the safety of QWO (CCH-aaes) for each study intervention in participants with cellulite.	• Proportion of participants reporting each treatment-emergent adverse events (TEAEs) throughout the study.
To assess the safety of QWO (CCH-aaes) for each study intervention in participants with cellulite.	• Proportion of participants reporting TEAEs of injection site reactions in the left buttock (investigational side) vs the right buttock (control side).
Exploratory	

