3.8.3. Investigator-Global Aesthetic Improvement Scale

At the time points indicated in the SoA (Table 3, Table 4, Table 5, and Table 6), the investigator will determine the degree of improvement of each buttock by comparing treated cellulite dimples from the Day 1 pre-treatment (Baseline) digital image of each buttock to the treated dimples observed in a live assessment (Table 9). I-GAIS will not be completed at Tx Visit 2 (Day 22) for the non-treated buttock for Cohorts 7a and 7b. Therefore, at Tx Visit 2 (Day 22) the I-GAIS will only be assessed for the investigational buttock (ie, left buttock) for Cohort 7a and only assessed for the control buttock (ie, right buttock) for Cohort 7b. For each buttock, the investigator will provide the rating from those below that best represents his/her answer.

Rating	Response Option	Description
+3	Very much improved	Optimal cosmetic result from treatment of the treated dimples
+2	Much improved	Marked improvement in the treated area appearance from before treatment, but not completely optimal
+1	Improved	Obvious improvement in the treated area appearance from before treatment, but additional treatment is indicated
0	No change	The treated area appearance is essentially the same as before treatment
-1	Worse	The treated area appearance is worse than before treatment
-2	Much worse	Marked worsening in appearance from the initial condition
-3	Very much worse	Obvious worsening in appearance from the initial condition

 Table 9:
 Investigator-Global Aesthetic Improvement Scale (I-GAIS)

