4.5.2. I-GAIS Ratings

The I-GAIS ratings are directly obtained from the investigator's assessment at Visit 6 (Day 22), Visit 11 (Day 43), Visit 16 (Day 90), Visit 17 (Day 135) and Visit 18 (Day 180) for Cohort 1-5. For Cohort 6, the I-GAIS ratings will be obtained at Visit 7 (Day 43), Visit 12 (Day 90), Visit 13 (Day 135) and Visit 14 (Day 180) and for Cohort 7, at Visit 6 (Day 22), Visit 11 (Day 43), Visit 16 (Day 64), Visit 21 (Day 90), Visit 22 (Day 135) and Visit 23 (Day 180).

A one-level I-GAIS responder for a treatment area (left buttock or right buttock) is defined as any participant with an improved (+1, +2 or +3) score on the I-GAIS at an analysis visit for that treatment area.

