- Method of Analyses: The one-level I-GAIS responders will also be summarized by treatment area for each cohort using frequency, proportion and corresponding 95% CI based on the Clopper-Pearson method for one-level I-GAIS responders. The summary tables will be provided for Cohort 1-5 at Visit 6 (Day 22), Visit 11 (Day 43), Visit 16 (Day 90), Visit 17 (Day 135) and Visit 18 (Day 180). For Cohort 6 at Visit 7 (Day 43), Visit 12 (Day 90), Visit 13 (Day 135) and Visit 14 (Day 180) and for Cohort 7 at Visit 6 (Day 22), Visit 11 (Day 43), Visit 16 (Day 64), Visit 21 (Day 90), Visit 22 (Day 135) and Visit 23 (Day 180).
- Supportive analysis to secondary endpoint: Not applicable.

I-GAIS ratings will be summarized for Cohort 1-5 at Visit 6 (Day 22), Visit 11 (Day 43), Visit 16 (Day 90), Visit 17 (Day 135), and Visit 18 (Day 180). For Cohort 6 at Visit 7 (Day 43), Visit 12 (Day 90), Visit 13 (Day 135), and Visit 14 (Day 180) and for Cohort 7 at Visit 6 (Day 22), Visit 11 (Day 43), Visit 16 (Day 64), Visit 21 (Day 90), Visit 22 (Day 135) and Visit 23 (Day 180) by treatment area for each of the cohorts. The I-GAIS ratings by participant at each visit will be listed.

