7.7.2. Adverse Events

All AE summary tables will include only TEAEs, unless otherwise specified. TEAEs will be summarized by SOC and PT. A participant will only be counted once per SOC and PT.

For TEAEs by severity grade (mild, moderate, severe), if a participant has multiple events occurring in the same SOC or same PT, then the event with the maximum intensity (ie, severe) will be counted

For TEAEs by relationship to study intervention, if a participant has multiple events occurring in the same SOC or same PT, the event with the highest association (ie, related) to study intervention will be summarized.

An overall summary of TEAEs and TEAEs related to study intervention will be presented and will include:

- Total number of TEAEs reported
- Total Number of TEAEs of Injection site reaction
- Total number of TEAEs reported by severity
- Participants with any TEAE
- Participants with TEAEs of Injection site reaction
- Participants with any serious TEAE

- Participants with any severe TEAE
- Participants with no severe TEAEs, but at least one moderate TEAE
- Participants with no severe TEAEs, but at least one mild TEAE
- Participants with any TEAEs leading to intervention interruption/discontinuation
- Participants with any TEAEs leading to withdrawal from study
- Participants with any TEAEs resulting in death

The following summary tables will be presented by SOC and PT:

- All TEAEs
- Study intervention related TEAEs
- TEAEs by severity
- Study intervention related TEAEs by severity
- Duration of study intervention related TEAEs
- Serious TEAEs

Refer to Table 17 for computation of duration of AEs. All TEAEs will be presented for Left Buttock, Right Buttock, Others (Not Applicable) and overall. For AEs where treatment location is neither Left Buttock nor Right Buttock will be collected as "Not Applicable" and is displayed under Others (Not Applicable) category.

The proportion of participants reporting TEAEs of injection site reaction in the left vs the right buttock will be summarized using frequency, proportion and corresponding 95% CI based on the Clopper-Pearson method.

The most common non-serious TEAEs by order of frequency (most frequent, 2nd most frequent, and 3rd most frequent) will be summarized by PT. The most common non-serious AEs are those with any PT that at least 5% of the participants reported at least once.

The following listings will be presented by participant:

- All AEs
- Fatal AEs
- Non-fatal serious AEs

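### I-GAIS and injection-site reactions get one interval per side and no paired side difference, and two Cohort 7 I-GAIS visits set sides with unequal prior doses next to each other

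*SAP*

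**What the plan says.** An I-GAIS responder is defined within one side (SAP 4.5.2: "A one-level I-GAIS responder for a treatment area (left buttock or right buttock) is defined as any participant with an improved" score). SAP 7.6.2.3 then plans: "The one-level I-GAIS responders will also be summarized by treatment area for each cohort using frequency, proportion and corresponding 95% CI", using Clopper-Pearson at each scheduled visit. It closes with "Supportive analysis to secondary endpoint: Not applicable". The same estimand names treatments to be compared but gives its population-level summary measure as not applicable.

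SAP 7.7.2 applies the same one-sample method to an endpoint worded as a side comparison: "The proportion of participants reporting TEAEs of injection site reaction in the left vs the right buttock".

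Protocol 5.3 says participants are their own controls for all endpoints in Cohorts 1 to 6, and in 7a and 7b for all endpoints except the primary.

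In Cohort 7 the sides are dosed 21 days apart. In 7a the left (investigational) side is treated on Days 1, 22 and 43, "with the control side treated with QWO (CCH-aaes) on Days 22, 43 and 64" (Protocol 5.1). In 7b the two schedules are swapped. SAP 3.8.3 allows for the stagger once: "I-GAIS will not be completed at Tx Visit 2 (Day 22) for the non-treated buttock for Cohorts 7a and 7b". SAP 7.6.2.2 matches Cohort 7 bruising by dose number, but SAP 7.6.2.3 tabulates I-GAIS by calendar visit.

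**The concern.** An intervention that lessens bruising is of limited use if it also lessens the cosmetic result, so a reader will compare the two sides. The planned output gives two marginal intervals that ignore the pairing and offers no interval for the difference. A real loss on the investigational side could look inconclusive, or a chance difference could look firm, depending on concordance that the table does not show.

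In Cohort 7 the same-day columns at Days 43 and 64 compare sides one dose apart. If response rises with dose number, part of the visible gap is dose count. The gap would favour the investigational side in 7a and the control side in 7b.

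**Working it through.** **Plan's own figures.** 7 x 30 = 210 participants, and 168/210 = 80% completers, or 168/7 = 24 per cohort if spread evenly (12 in each of 7a and 7b). The documents give no response rate, power, margin or precision for I-GAIS, so the rates below are assumptions.

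**Do the marginal intervals determine the paired result?** Assume n = 30, right 25/30 and left 17/30. The planned output is:
- right 83.3%, Clopper-Pearson 65.3 to 94.4
- left 56.7%, Clopper-Pearson 37.4 to 74.5

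The intervals overlap. Let b be the pairs where only the right side responds and c those where only the left does. The margins fix b - c = 25 - 17 = 8, so the difference (right minus left) is 8/30 = 26.7 points. They do not fix b + c. The number of pairs with both sides responding is 17 - c, and with neither 5 - c, so c can be 0 to 5. The results for all six patterns, using the Tango score interval and the exact McNemar test, are:

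| b / c | Paired 95% CI (points) | McNemar p |
|---|---|---|
| 8 / 0 | 12.3 to 44.4 | 0.008 |
| 9 / 1 | 7.2 to 45.7 | 0.021 |
| 10 / 2 | 4.6 to 46.8 | 0.039 |
| 11 / 3 | 2.4 to 48.0 | 0.057 |
| 12 / 4 | 0.6 to 49.1 | 0.077 |
| 13 / 5 | -1.1 to 50.2 | 0.096 |

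The planned table is identical for all six. If the sides were independent, b would be about 25 x 13/30 = 10.8 and c about 17 x 5/30 = 2.8, close to the 11 / 3 row. Pairing tightens the interval only when the sides agree more than that.

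**Cohort 7 doses before each I-GAIS reading.** Treatment-day readings precede that day's injection (footnote h, Protocol 2.8 and 2.9). Counting dosing days earlier than the visit, left vs right:

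| Visit (day) | 7a doses | 7b doses | Days since last dose, 7a | Days since last dose, 7b |
|---|---|---|---|---|
| V6 (22) | 1 vs not rated | not rated vs 1 | 21 vs none | none vs 21 |
| V11 (43) | 2 vs 1 | 1 vs 2 | 21 vs 21 | 21 vs 21 |
| V16 (64) | 3 vs 2 | 2 vs 3 | 21 vs 21 | 21 vs 21 |
| V21 (90) | 3 vs 3 | 3 vs 3 | 47 vs 26 | 26 vs 47 |
| V22 (135) | 3 vs 3 | 3 vs 3 | 92 vs 71 | 71 vs 92 |
| V23 (180) | 3 vs 3 | 3 vs 3 | 137 vs 116 | 116 vs 137 |

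Both sides are read after unequal doses at two of six visits. If each added dose raised the responder proportion by d points, left minus right at Days 43 and 64 would shift by +d in 7a and -d in 7b. The documents give no d. An assumed 10 to 20 would shift the gap by 10 to 20 points.

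**Precision of a paired difference.** Near zero difference, the half-width is about 1.96 x sqrt(discordant fraction / n). For discordance of 10% to 50% this is 11 to 25 points at n = 30, and 16 to 36 at n = 15.

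**The case against.** The strongest reply is that no comparative I-GAIS objective exists. SAP Table 1 says "To assess the level of aesthetic improvement of cellulite after treatment with QWO (CCH-aaes", and Protocol 10.3.1 plans a description by treatment area. A per-side proportion with an exact interval answers that, no retention margin is stated, and the line naming treatments to be compared is generic text repeated across estimands. This stands against any claim that the secondary objective is unanswered. It does not dispose of the own-control statement in Protocol 5.3, or of the injection-site endpoint, which is worded left versus right.

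A reader might infer that all Cohort 7 I-GAIS results are distorted by dose count. The schedule does not support that: Day 22 is one-sided by rule, and Days 90, 135 and 180 are 3 vs 3. The SAP also plans no I-GAIS side difference, so the distortion arises only when a reader subtracts the columns.

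A reader might also infer that the Cohort 6 rationale (Protocol 5.2: "to determine whether there will be a decrease in bruising while experiencing an improvement in cellulite") requires a joint bruising and I-GAIS tabulation. It is rationale, not an endpoint. Bruising and I-GAIS are each tabulated and listed by participant, and no passage links Visit 3 bruising to a later I-GAIS visit.

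Finally, the exploratory section is redacted and the table shells are in SAP Module 2, which was not available. The absence of a paired analysis can be stated for the visible text only.

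**Conclusion.** The concern holds in a limited form. In the visible SAP text, I-GAIS responders and injection-site TEAEs have no within-participant side difference, and the planned intervals cannot supply one. In the assumed example, the same table is compatible with a paired interval well clear of zero and with one that crosses it. That example rests on assumed rates, and the benefit of pairing depends on a concordance the documents do not give. For Cohorts 1 to 6 this is the whole point, because both sides are dosed on the same days.

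For Cohort 7 there is a further mismatch of one dose at Days 43 and 64, and a 21-day offset in time since the last dose from Day 90 on. Its existence follows from the schedule, but its effect on response is unknown.

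The documents do not support the reading that the plan would hide a known loss of benefit, or that an intervention's effect on cellulite goes unreported: proportions and ratings appear for both sides. This is a worthwhile improvement to descriptive secondary endpoints. The primary bruising endpoint, which is already a within-participant comparison, is not affected.

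**What to change.** In SAP 7.6.2.3, add for each cohort and visit the paired left-minus-right difference in I-GAIS responders with a paired 95% CI, for example the Tango score interval. (The illustration above is right minus left, so its signs reverse.) In SAP 7.7.2, add the same paired difference for injection-site TEAEs, per cohort.

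For Cohort 7, make the I-GAIS side comparison before Day 90 by dose number:
- 7a: left V6 with right V11; left V11 with right V16; left V16 with right V21.
- 7b: left V11 with right V6; left V16 with right V11; left V21 with right V16.

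The first two pairs in each list are both 21 days after the dose. Footnote that the third is 21 vs about 26 days, and that same-day comparisons at Days 90, 135 and 180 carry a 21-day offset.

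The cost is SAP wording and a few table rows, since the SAP already schedules these readings. The intervals will be wide at n = 15 to 30 and should be presented as descriptive. If the redacted exploratory section or Module 2 already contains a paired analysis, a cross-reference may be enough for that part.

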7.6.3. Exploratory Efficacy Analysis

e evnlor	ratory estin	nand is de	efined by	the follow	vina:		
c exploi	atory estin	mana is ac	Tilled by	the follow	mg.		
•							
•							
•							
•							
•							

• **Intercurrent Event:** Not applicable.

• **Population Level-Summary measure:** Not applicable.

• Supportive analysis to primary endpoint: Not applicable.

7.7. Safety Analyses

Safety data will be summarized by treatment area (left and right buttock) and overall, for each of the 7 cohorts using the Safety Population.

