7.1. Selection and Marking of Dimples

To ensure that the non-interventional buttock can serve as a control, and that a similar level of injection site bruising may be expected, participants should have a similar number of dimples requiring treatment on each buttock. Participants in Cohorts 1, 2, 3, 5, and 6 can be treated with up to 12 injections of QWO (CCH-aaes) on each buttock. The number of injections of QWO (CCH-aaes) administered to the right and left buttocks should be identical on Day 1. The number of injections may differ following the first treatment session, eg, 12 injections in each buttock in the first treatment session followed by fewer injections per buttock at the second and third treatment sessions as dimples improve.

Participants in Cohort 7 can be treated with up to 12 injections of QWO (CCH-aaes) on each buttock. Dimples will only need to be marked on the days of treatment. In Cohort 7a, on Day 1 only, the investigational buttock will be treated with QWO (CCH-aaes) and on Day 64 only the control buttock will be treated with QWO (CCH-aaes). On Days 22 and 43, both buttocks will be treated with QWO (CCH-aaes). In Cohort 7b, on Day 1, only the control buttock will be treated with QWO and on Day 64, only the investigational buttock will be treated with QWO (CCH-aaes). On Days 22 and 43, both buttocks will be treated with QWO (CCH-aaes).

For treatment, a qualified designated physician will select up to 12 dimples within each treatment area (each buttock) that are well-defined, evident when the participant is standing, and suitable for treatment.

For each dimple selected for treatment, a qualified designated physician will choose injection sites (injection sites within a dimple should be spaced approximately 2 cm apart, if a dimple requires more than 1 injection; locating at least 1 injection site at the nadir, if present, of the dimple). Each injection site will be marked with a "dot" using a surgical marker. For round dimples, the "dot" will be placed in the center of the dimple; for elongated dimples, "dots" will be spaced out approximately 2 cm along the longer axis of the dimple. The qualified designated physician will then use a surgical marker to circle each of the dimples selected for treatment.

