8. DISCONTINUATION FROM STUDY INTERVENTION AND STUDY WITHDRAWAL

8.1. Discontinuation of Study Intervention

In certain instances, it may be necessary for a participant to be permanently discontinued from study intervention (QWO [CCH-aaes]) by the investigator or the sponsor. Treatment may be discontinued at the discretion of the investigator for safety, behavioral, or compliance reasons. This is expected to be uncommon.

Participants who request to discontinue study intervention will be encouraged to complete the remaining study visits and evaluations and provide any additional follow-up information as required by the study. Participants who discontinue from the study intervention and do not agree to remain in the study for follow-up, will be requested, (if applicable) to complete an ET visit and a 28-day post-treatment Safety Follow-up Visit (or phone call if a visit is not possible), if applicable. During this visit, the status of any ongoing AEs/SAEs, or the occurrence of any new AEs/SAEs will be recorded.

The date of and reason for discontinuation of study intervention will be recorded.

Participants who discontinue from study intervention at any time after the first dose of study QWO (CCH-aaes) will not be replaced.

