5. ANALYSIS POPULATIONS

The study will use the following analysis populations for data summaries.

Table 16: Analysis Populations

Population Definition		Analysis	
Safety Population	The Safety Population is defined as all participants who received at least 1 injection of QWO (CCH-aaes).	All safety analyses will be based on this population	
Full Analysis Set (FAS)	The Full Analysis Set is defined as all participants in the Safety Population who have at least 1 valid IABSS assessment at a treatment area after an injection of QWO (CCH-aaes).	All efficacy analyses will be based on this population.	

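### In Cohort 7, a participant who stops before Day 22 is counted as free of injection-site reactions on a buttock that was never injected

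*SAP*

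**What the plan says.** The analysis sets are defined per participant. Under SAP 5 the Safety Population is "all participants who received at least 1 injection of QWO (CCH-aaes", on either side. The Full Analysis Set takes those in the Safety Population "who have at least 1 valid IABSS assessment at a treatment area after an injection of QWO (CCH-aaes", so again one side is enough.

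The safety tables are per side. SAP 7.7 states: "Safety data will be summarized by treatment area (left and right buttock) and overall, for each of the 7 cohorts using the Safety Population". SAP 7.7.2 adds: "The proportion of participants reporting TEAEs of injection site reaction in the left vs the right buttock will be summarized using frequency", together with the proportion and a Clopper-Pearson 95% interval. Protocol 4.1 and SAP Table 1 list this left-versus-right comparison as a secondary endpoint.

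Cohort 7 staggers the sides. Under Protocol 7.1 and 7.2.10, 7a receives the first injection in the left (investigational) buttock on Day 1 and in the right (control) buttock on Day 22. The order is reversed in the other sub-cohort: "In Cohort 7b, on Day 1, only the control buttock will be treated with QWO".

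For I-GAIS, SAP 3.8.3 says: "I-GAIS will not be completed at Tx Visit 2 (Day 22) for the non-treated buttock for Cohorts 7a and 7b".

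**The concern.** In Cohorts 1 to 6 both buttocks are injected on Day 1, so membership of the Safety Population implies exposure on both sides and a shared denominator does no harm. Amendment 02 added a cohort where that no longer follows. Between Day 1 and Day 22 a Cohort 7 participant has one exposed buttock and one that cannot have an injection-site reaction. If she stops in that interval she stays in the Safety Population, and nothing in the SAP takes her unexposed buttock out of the denominator.

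The affected side differs between the sub-cohorts. In 7a the control proportion falls, which makes the tranexamic acid side look worse. In 7b the investigational proportion falls, which makes it look better. Since SAP 7.7 speaks of 7 cohorts, 7a and 7b could be pooled. Pooling would hide part of the contrast error and leave both side-level proportions too low.

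**Working it through.** **Inputs**
- Enrolment 210, at least 168 completers (SAP 3.6); 15 in each of 7a and 7b (SAP Table 2).
- Bruising reported in 84% of subjects (Protocol 3.3.1). This is a per-subject figure from participants treated in both buttocks. Using it as the rate p on each injected side is an assumption.
- Denominator rules in SAP 6.1: non-missing values, and evaluable participants, a term left undefined.

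**Step 1: the plan's own figures.** 6 × 30 + 15 + 15 = 210, and 168/210 = 0.80. Non-completion of 42/210 = 20% is therefore implied; no attrition rate is stated. Spread evenly over cohorts, this is 0.20 × 15 = 3 per sub-cohort.

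**Step 2: follow one participant.** She is in 7a, is injected on the left on Day 1 and stops before Day 22. She is in the Safety Population. On the right she has no injection and so no possible injection-site reaction. An adverse event that did not occur is not a missing value, so the non-missing rule keeps her. She adds 1 to the right-side denominator and can add nothing to the numerator.

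**Step 3: size.** With n = 15 and d participants stopping before Day 22, the expected proportion on the later-treated side is p × (n − d)/n, and the shortfall is p × d/n. On participants injected in that buttock the expectation is 84% for every d.

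| d | 0.84 × (15 − d)/15 | Shortfall (points) |
|---|---|---|
| 0 | 84.0% | 0 |
| 1 | 78.4% | 5.6 |
| 2 | 72.8% | 11.2 |
| 3 | 67.2% | 16.8 |

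The last row puts all of the implied attrition before Day 22.

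**Step 4: how likely.** With 20% attrition uniform over 180 days, 0.20 × 21/180 = 2.3% stop before Day 22. That is 0.35 of 15 expected, and a mean shortfall of 0.84 × 2.33% = 1.96 points. The chance of at least one in a sub-cohort is 1 − (1 − 0.0233)^15 = 0.30, so none is the likeliest result. At early-stopping rates of 5%, 10% and 20% the chance is 0.54, 0.79 and 0.97.

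**Step 5: in counts (Clopper-Pearson 95%).**
- d = 1: 12/14 = 85.7% (57.2 to 98.2) becomes 12/15 = 80.0% (51.9 to 95.7).
- d = 3: 10/12 = 83.3% (51.6 to 97.9) becomes 10/15 = 66.7% (38.4 to 88.2).

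**Step 6: pooling.** With one early stopper in each sub-cohort and n = 30, each side loses 0.84 × 1/30 = 2.8 points. The left-right difference is unaffected, but both sides are expected at 81.2% instead of 84%.

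**Step 7: I-GAIS.** At Day 22 the untreated buttock is not rated, so under SAP 6.1 its denominator is 0. Later visits are not covered. Protocol 8.1 says: "Participants who request to discontinue study intervention will be encouraged to complete the remaining study visits and evaluations", and I-GAIS is scheduled at the EOS/ET visit. A never-injected buttock could be rated there and would enter as non-missing. Separately, SAP Table 6 has a single I-GAIS row for 7b, marked at Day 22 and footnoted as assessed for each buttock separately. That does not agree with SAP 3.8.3.

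**The case against.** The strongest reply is that the SAP need not be read this way. SAP 6.1 also bases denominators on evaluable participants, and a buttock without an injection could be called not evaluable for an injection-site reaction. The table shells and code are in SAP Module 2, which is not among these documents and may settle the matter. What stands is that the reading is possible. It does not close the gap, because the word is undefined and SAP 7.7 names the population for side-level tables outright.

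The consequence is also limited. The comparison is descriptive, the intervals above overlap heavily, and SAP 7.7.1 already tabulates the number treated at each visit by side, so a careful reader could spot a shortfall. Protocol 8.2 allows extra enrolment and Protocol 8.3 allows replacement of those lost to follow-up. Either could push the effect per person below 1/15, though neither removes the early stopper from the set. These points hold and keep the matter modest.

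On I-GAIS, SAP 3.8.3 rates treated dimples, and a never-injected buttock has none. That makes a later rating less likely, but no rule excludes one.

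**Conclusion.** The gap is real for injection-site reactions. The stated denominator lets an impossible event count as an absent one for anyone in Cohort 7 who stops before Day 22. The error is zero with no such participant and about 5.6 points for each one out of 15. About 2 points are expected under uniform attrition, and 16.8 is the ceiling. These sizes rest on the assumed 84% per injected side, the back-calculated 20% attrition shared evenly over cohorts, and the assumed timing.

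Two stronger readings are tempting, and the documents do not support them.
- A reader might infer that the later-treated side is understated by design. It is not: everyone who continues is injected on both sides from Day 22, so the error needs staggering and early stopping together.
- A reader might infer from the single row in SAP Table 6 that untreated buttocks are scored as I-GAIS non-responders at Day 22, for instance a pooled left side of 7/15 (46.7%) printed as 7/30 (23.3%). That would require sites to disregard SAP 3.8.3 and the tables to pool 7a with 7b. No non-responder imputation is specified. The I-GAIS issue is confined to later or ET ratings of a never-injected buttock and to the mismatch between Table 6 and SAP 3.8.3.

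**What to change.** 1. In SAP 7.7.2, state that for Cohorts 7a and 7b the denominator of every side-level summary of injection-site TEAEs is the participants with at least 1 QWO injection in that buttock. Show 7a and 7b separately in these tables.
2. In SAP 7.6.2.3, extend the exclusion in SAP 3.8.3 to any later or ET I-GAIS rating of a buttock never injected; such ratings are listed only.
3. In SAP Table 6, split the 7b I-GAIS row by buttock, as SAP Table 5 already does for 7a. Keep the Day 22 mark for the control side and drop it for the investigational side. Deleting the mark from the single row would lose the control-side rating that SAP 3.8.3 requires.

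The cost is SAP wording and one derived flag per buttock. Protocol 7.2.2 and 7.4 already have injection numbers and dosing recorded, and SAP 7.7.1 already summarizes exposure by side. No clinical rule changes. The small downside is that left and right denominators may differ slightly, which a footnote can explain.
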